10.1.11 CONFLICT OF INTEREST POLICY

The independence of this study from any actual or perceived influence is critical. None of the persons who have a role in the design, conduct, analysis, publication, or any aspect of this trial have a conflict of interest. Should one develop, or be perceived to be present, it will be managed by following the CHKD Human Subjects Research – Conflict of Interest Policy C1108 and the EVMS IRB Conflict of Interest Policies.²⁵

10.2 ABBREVIATIONS

ADLs	Activities of Daily Living
AE	Adverse Event
ANCOVA	Analysis of Covariance
CFR	Code of Federal Regulations
CHKD	Children's Hospital of the King's Daughters
CITI	Collaborative Institutional Training Initiative
CMP	Clinical Monitoring Plan

CRF	Case Report Form
DHHS	Department of Health and Human Services
DSP	Dexamethasone Sodium Phosphate
eCRF	Electronic Case Report Forms
FACES	Wong Baker Faces Pain Scale
FDA	Food and Drug Administration
GEE	Generalized Estimation Equation
GLM	Generalized Linear Model
HEP	Home Exercise Program
HIPAA	Health Insurance Portability and Accountability Act
HRC	Hospital Research Coordination
ICMJE	International Committee of Medical Journal Editors
IE	Initial Evaluation
IND	Investigational New Drug Application
IRB	Institutional Review Board
ISM	Independent Safety Monitor
LAR	Legally Authorized Representative
LEFS	Lower Extremity Function Scale
OHRP	Office for Human Research Protections
OSD	Osgood Schlatter Disease
PI	Principal Investigator
PT	Physical Therapy
QA	Quality Assurance
QC	Quality Control
RTS	Return To Sport
SAE	Serious Adverse Event
SAP	Statistical Analysis Plan
SLJ	Sinding-Larsen-Johansson
SM	Sports Medicine
SoA	Schedule of Activities
UP	Unanticipated Problem

10.3 PROTOCOL AMENDMENT HISTORY

Version	Date	Description of Change	Brief Rationale
2.0	2018_08_27	Added IND#; Added language	
		regarding potential burns;	
		Revised inclusion criteria; Revised	
		exclusion criteria; Revised	
		preparation of study treatment;	
		Added burn-specific AE	
		monitoring and post-patch	
		application AE monitoring; Added	
		language regarding IND Safety	
		Reporting; Clarified "Pain free"	
		criteria for RTS; Added additional	
		adverse event reporting	
		requirements	
3.0	2018_09_18	Clarified data handling of 90-day	
		electronic survey and added	
		actual 90-Day Follow Up REDCap	
		Survey	
4.0	2019_07_11	Lowered inclusion age to 7;	
		added two study sites; raised	
		estimated time to meet study	
		enrollment; added email	
		reminders	
5.0	2019_08_15	Added language differentiating	
		between first time patch	
		application monitoring and	
		subsequent patch application	
		monitoring.	
6.0	2020_05_20	Added language for conducting	
		interim analyses; removed two	
		(2) Investigators who left the	
		organization.	

12 APPENDICES

12.1 LOWER EXTREMITY FUNCTIONAL SCALE (LEFS)

Lower Extremity Functional Index

We are interested in knowing whether you are having any difficulty at all with the activities listed below because of your lower limb problem for which you are currently seeking attention. Please provide an answer for each activity.

Today, do you or would you have any difficulty at all with:

Activities	Extreme Difficulty or unable to perform activity	Quite a bit of difficulty	Moderate difficulty	A little bit of difficulty	No difficulty
a. Any of your usual work, housework or school activities.	0	1	2	3	4
b. Your usual hobbies, recreational or sporting activities	0	1	2	3	4
c. Getting into or out of the bath.	0	1	2	3	4
d. Walking between rooms.	0	1	2	3	4
e. Putting on your shoes or socks.	0	1	2	3	4
f. Squatting.	0	1	2	3	4
g. Lifting an object, like a bag of groceries from the floor.	0	1	2	3	4
h. Performing light activities around your home.	0	1	2	3	4
i. Performing heavy activities around your home.	0	1	2	3	4
j. Getting into or out of a car.	0	1	2	3	4
k. Walking 2 blocks.	0	1	2	3	4
I. Walking a mile.	0	1	2	3	4
m. Going up or down 10 stairs (about 1 flight of stairs).	0	1	2	3	4
n. Standing for 1 hour.	0	1	2	3	4
o. Sitting for 1 hour.	0	1	2	3	4
p. Running on even ground.	0	1	2	3	4
q. Running on uneven ground.	0	1	2	3	4
r. Making sharp turns while running fast.	0	1	2	3	4
s. Hopping.	0	1	2	3	4
t. Rolling over in bed.	0	1	2	3	4
COLUMN TOTALS					

(Circle one number on each line)

Score variation ± 6 LEFTS points MDC & MCID = 9 LEFS points

Score ____/80

12.2 WONG BAKER FACES PAIN SCALE

12.3 RETURN TO SPORT CHECKLIST

Phase 1 - Nonimpact

. Pain-free ADL's

□Squats x 10 pain-free with proper mechanics (all of the following must be met:)

□No anterior tibial translation

□ Heels stay in contact with the ground

□Neutral/slight external rotation foot placement

 \Box Knee stays in line with 2nd toe

□Trunk upright

□No trunk shift

NOTE: Must meet both Phase 1 criteria before progressing to Phase 2 criteria. Phase 2 criteria must be assessed/completed in the order listed below.

Phase 2 - Impact

Broad jumps x10 pain-free with proper mechanics (all of the following must be met:)

□Knee in line with 2nd toe on take-off and landing

□No anterior tibial translation on landing

□Even footing on take-off and landing

□Soft landing

□ Pain free

□Single leg triple hop for distance (all of the following must be met:)

□ Met all above criteria for broad jumping

 \Box No loss of balance

 \Box No extra hop on landing

□No touching down of either the contralateral lower extremity or the upper extremity

□Stick and hold final landing for at least 3 seconds

□Affected lower extremity within 85% of the unaffected lower extremity

□ Pain-free

□ Modified T-test

□ Met all above criteria for single leg triple hop for distance

 \Box 100% effort

 \Box Pain-free

12.4 GODIN LEISURE-TIME EXERCISE QUESTIONNAIRE

Godin Leisure-Time Exercise Questionnaire

 During a typical 7-Day period (a week), how many times on the average do you do the following kinds of exercise for more than 15 minutes during your free time (write on each line the appropriate number).

> Times Per Week

a) STRENUOUS EXERCISE

(HEART BEATS RAPIDLY)

(e.g., running, jogging, hockey, football, soccer, squash, basketball, cross country skiing, judo, roller skating, vigorous swimming, vigorous long distance bicycling)

b) MODERATE EXERCISE

(NOT EXHAUSTING)

(e.g., fast walking, baseball, tennis, easy bicycling, volleyball, badminton, easy swimming, alpine skiing, popular and folk dancing)

c) MILD EXERCISE

(MINIMAL EFFORT)

(e.g., yoga, archery, fishing from river bank, bowling, horseshoes, golf, snow-mobiling, easy walking)

During a typical 7-Day period (a week), in your leisure time, how often do you engage in any regular activity long enough to work up a sweat (heart beats rapidly)?

OFTEN	SOMETIMES	NEVER/RARELY
1. 0	2. 🛛	3. 🛙

12.5 30-DAY PHONE FOLLOW UP

The treating therapist may choose to send the subject's guardian a reminder email prior to the 30-day phone follow-up to confirm date, time, and number to call, as well as to remind the subject to complete the LEFS and GLTAQ prior to the call. An electronic copy of the LEFS and GLTAQ will be included in the email in case the subject misplaced their copy provided at the Clinic Visit Check.

The following information will be gathered at the 30-day phone follow-up call:

Date of Call:

Adverse Events

Ongoing: Review Adverse Event Log to determine if there were any unresolved AEs from last clinic visit.

If yes, ask about AE to determine whether severity changed, if AE resolved, or if any new intervention was required.

Complete AE Log

New: Question: Since your last clinic visit, have you been seen by a doctor or had any new medical problems?

If yes, complete entry on AE Log

Concomitant Medications

Ongoing: Review current medications to confirm no change to drug, dose, and frequency

New: Question: Since your last clinic visit, have you started any new medications?

If yes, document drug, date started, reason for taking (if an AE, complete entry on AE Log), dose, frequency

Administer the LEFS

Administer the Godin Leisure-Time Activity Questionnaire

12.6 90-DAY FOLLOW UP (ELECTRONIC SURVEY)

90-Day Follow Up		Page 1 of 2
Please complete the survey below.		
Thank you!		
First Name		
Last Name		-
Today's date		
GODIN LEISURE-TIME EXERCISE QUESTIONNAIRE		
1 Rusian - Emiral 7 Rev - reid (surve), how -		u de Me
 During a typical 7-Day period (a week), now ma following kinds of exercise for more than 15 minu 	any times on the average do yo ites during your free time.	ou do the
 a) STRENUOUS EXERCISE (HEART BEATS RAPIDLY) (e.g., running, jogging, hockey, football, soccer, squash, basketball, cross country skiing, judo, roller skating, vigorous swimming, vigorous long distance bicycling) 	(Times Per Week)	-
b) MODERATE EXERCISE (NOT EXHAUSTING) (e.g., fast walking, baseball, tennis, easy bicycling, volleyball, badminton, easy swimming, alpine skiing, popular and folk dancing)	(Times Per Week)	
c) MILD EXERCISE (MINIMAL EFFORT) (e.g. yoga, archery, fishing from river bank, bowling, horseshoes, golf, snow-mobiling, easy walking)	(Times Per Week)	
 During a typical 7-Day period (a week), in your leisure time, how often do you engage in any regular activity long enough to work up a sweat (heart beats rapidly)? 	O 1. OFTEN O 2. SOMETIMES O 3. NEVER/RARELY	
Did you have any ongoing medical problems at your 30-day Follow Up call?	O Yes O No	
Did you have any ongoing medical problems at your 30-day Follow Up call? What is the ongoing medical problem?	O Yes O No	
Did you have any ongoing medical problems at your 30-day Follow Up call? What is the ongoing medical problem? Has this medical problem gone away?	○ Yes ○ No ○ Yes ○ No	-
Did you have any ongoing medical problems at your 30-day Follow Up call? What is the ongoing medical problem? Has this medical problem gone away? What date did this medical problem go away?	O Yes ○ No 	-
Did you have any ongoing medical problems at your 30-day Follow Up call? What is the ongoing medical problem? Has this medical problem gone away? What date did this medical problem go away? Your physical therapist will be calling you to follow up on the medical problem. Please provide the best phone number for us to reach you.	O Yes No O Yes O No	-
Did you have any ongoing medical problems at your 30-day Follow Up call? What is the ongoing medical problem? Has this medical problem gone away? What date did this medical problem go away? Your physical therapist will be calling you to follow up on the medical problem. Please provide the best phone number for us to reach you. Since your 30-day follow up call, have you been seen by a doctor or had any new medical problem?	O Yes O Yes O No O Yes O Yes O Yes O Yes No	-

Confidential

Page 2 of 2

Your physical therapist will be calling you to follow up on the medical problem. Please provide the best phone number for us to reach you.

Since your 30-day Follow Up call, have you started any new medications?

What is the name of your new medication?

Please explain why you are taking this new medication (for example, "It is because I have a cold")?

Your physical therapist may call you to follow up on the new medications you are taking. Please provide the best phone number for us to reach you. _____

O Yes O No

.....

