4 STUDY DESIGN

4.1 OVERALL DESIGN

The primary study hypothesis is that the time to achieve RTS criteria for pediatric patients with apophysitis of the knee who receive iontophoresis with DSP treatment and PT will be different than those who receive placebo or PT alone. The secondary study hypotheses are: that the patient reported outcomes for pediatric patients with apophysitis of the knee who receive iontophoresis with DSP treatment and PT will be different than those who receive placebo or PT alone; and the frequency and intensity of adverse events among pediatric patients with apophysitis of the knee who receive placebo or PT alone.

This is a Phase II trial. It is a three-arm, randomized, double-blind, placebo-controlled comparison study looking at the functional and patient reported outcomes of iontophoresis (with DSP or placebo) in conjunction with PT versus PT alone to treat pediatric patients diagnosed with apophysitis of the knee.

The study is double-blinded and placebo-controlled to minimize bias. There will be three (3) study groups

- Iontophoresis using DSP (study drug) + PT
- Iontophoresis using placebo + PT
- o PT alone

Participants in all three groups will receive the standard PT protocol for apophysitis of the knee. This will involve up to 20 visits. Participants randomized to the iontophoresis groups will receive up to 12 iontophoresis treatments over a maximum of eight (8) weeks. All participants will receive a phone follow-up call 30 days after they meet RTS criteria as well as an electronic survey follow-up 90 days after they meet RTS criteria.

This study will only be conducted through the Children's Hospital of the King's Daughters Sports Medicine PT Department with study-related activities occurring at six of CHKD's Hampton Roads PT clinics. All study-related activities will be completed by Physical Therapists and Physical Therapist Assistants (Treating Therapists) trained on the protocol and CITI trained.

Concomitant therapies, age, gender, and race will be conducted to analyze the possible effects of these covariates on length of time to RTS

Stratifications of age, gender, and race will be conducted to analyze the possible effect of these covariates on length of time to RTS as well as on patient reported outcomes LEFS, Godin Leisure-Time Activity, and FACES Pain Scale and on safety outcomes.

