8 STUDY ASSESSMENTS AND PROCEDURES

8.1 EFFICACY ASSESSMENTS

As Standard of Care:

- All patients who are referred to the participating PT clinics with a diagnosis of apophysitis of the knee and a prescription for PT with iontophoresis will receive a PT Initial Evaluation (IE).
 Per department policy, the PT IE must take place within 90 days of referral date as indicated on the script.
 - The IE includes: review of demographics, medical history, medication regime, strength and balance tests, pain assessment, review of home exercise program, icing instructions, activity restrictions, and bracing and NSAID instructions as recommended by their referring physician.
- After the IE, and as part of standard of care, all participants, regardless of group assignment, will receive a standardized PT treatment progression provided by qualified therapists.
 - As standard of care, PT progression visits may include up to 19 visits
- Clinic Check Visit Two (2) to three (3) business days after a participant is cleared for RTS, or has received treatment for eight (8) weeks, whichever is sooner, the participant will return to the

clinic for the Treating Therapist to confirm the participant remains pain free and able to meet the RTS criteria.

• Physical therapy progression visits to further fine tune mechanics, strength, and stretch may occur after this visit as part of their standard of care.

Study-related:

Study-related procedures will begin on the first PT Treatment Day, which may be the same day as the IE or at the next PT visit, but never before the Consent is signed. If subjects meet inclusion/exclusion criteria and the potential participant consents to participate at the Initial PT Evaluation Visit, the IE and Enrollment/Randomization Study Treatment Visit 1 visits may be combined.

The following procedures/evaluations will be obtained by the Treating Therapists:

- Lower Extremity Function Scale (LEFS) (see Appendix 12.1) a patient reported paper-based questionnaire that asks the patient to choose the level of difficulty of completing 20 different activities. Assessed at Study Treatment Visits 1, 5, 12/RTS Criteria Met Visit, and 30-day Follow Up. Note: the LEFS will be administered over the phone at the 30-day Follow-Up Visit.

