8.3.4 TIME PERIOD AND FREQUENCY FOR EVENT ASSESSMENT AND FOLLOW-UP

The occurrence of an AE or serious adverse event (SAE) may come to the attention of study personnel during study visits, during the 30-day follow up phone call or from the 90-day electronic survey. AEs will be assessed at each treatment visit through the performance of a brief physical exam, interview by the Treating Therapist, review of concomitant medications, as well as from patient-reported responses to the FACES Pain scale and LEFS (assessed only at Study Treatment Visit 1, 5, 12, and 30-day follow-up).

All AEs including local and systemic reactions not meeting the criteria for SAEs will be captured on the appropriate case report form (CRF). Information to be collected includes event description, time of onset, clinician's assessment of severity, relationship to study product (assessed only by those with the training and authority to make a clinical assessment), expectedness, and time of resolution/stabilization of the event. All AEs occurring while on study will be documented appropriately regardless of relationship. All AEs will be followed to adequate resolution or stabilization.

Any medical condition that is present at the time that the participant is screened will be considered as baseline and not reported as an AE. However, if the study participant's condition deteriorates at any time during the study, it will be recorded as an AE.

Changes in the severity of an AE will be documented to allow an assessment of the duration of the event at each level of severity to be performed. AEs characterized as intermittent require documentation of onset and duration of each episode.

The treating Therapist will record all reportable events with start dates occurring any time after informed consent is obtained until 90 days after RTS criteria met or participant has received study treatment for eight (8) weeks, whichever is the shorter of the two time periods. At each study visit, the treating Therapist will inquire about the occurrence of AE/SAEs since the last visit. Events will be followed for outcome information until resolved or deemed by PI and Independent Safety Monitor as chronic or stable.

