9.4.4 SAFETY ANALYSES

A GEE model will be conducted to estimate likelihood of occurring and intensity of adverse events for Pediatric patients with apophysitis of the knee who receive iontophoresis with DSP treatment and PT as compared to those who receive placebo or PT alone.

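### The 30-day call asks about new problems since an undated last clinic visit, so for children who have PT after the Clinic Check the adverse event question can cover less than the intended 25–28 days.

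*Combined protocol and SAP*

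**What the plan says.** Appendix 12.5 gives the therapist's script for the 30-day call. The question on new events is "Since your last clinic visit, have you been seen by a doctor or had any new medical problems". The new-medication question uses the same anchor, as does the review of unresolved entries on the AE Log. None of the three names the visit or gives its date.

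Section 8.1 places the Clinic Check "Two (2) to three (3) business days after a participant is cleared for RTS", or after eight weeks of treatment if sooner. It then adds: "Physical therapy progression visits to further fine tune mechanics, strength, and stretch may occur after this visit as part of their standard of care". Section 4.1 describes the standard PT protocol for all three groups: "This will involve up to 20 visits". Section 8.1 puts the allowance after the initial evaluation this way: "PT progression visits may include up to 19 visits".

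On when events are asked about, Section 8.3.4 says: "At each study visit, the treating Therapist will inquire about the occurrence of AE/SAEs since the last visit". The Schedule of Activities and Section 8.2 place AE evaluation at the study treatment visits, the Clinic Check, the 30-day call and the 90-day survey. The Schedule adds the early stop visit. Neither has an entry for PT visits after the Clinic Check.

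The 90-day survey (Appendix 12.6) asks about problems ongoing at the 30-day call, and about new problems and new medications since that call.

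Safety is a secondary endpoint compared between groups. Section 9.4.4 states: "A GEE model will be conducted to estimate likelihood of occurring and intensity of adverse events".

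**The concern.** The last scheduled in-person AE inquiry is the Clinic Check, but the next question starts from whichever visit the family takes to be the last one. If the child is still attending PT in the same clinics, the plain meaning is the latest PT visit. The days between the Clinic Check and that visit then fall outside the question.

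Two things are at stake. First, some new events in the month after the last patch may not be prompted. Section 2.3.1.2 says there are no published data on systemic effects of dexamethasone given by iontophoresis, so capture in that month has some value. Second, the length of the elicited window would depend on PT use after randomisation. Later PT plausibly follows recovery, which the treatment is meant to change, so the window could differ between the arms that Section 9.4.4 compares. Section 7.1 adds another route to later visits: a child whose pain returns after the Clinic Check gets standard care, and Section 8.3.4 counts deterioration during the study as an AE.

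**Working it through.** The plan states no figure for the recall window, so there is none to reproduce. The check is calendar arithmetic for a child who meets the return-to-sport (RTS) criteria.

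**Inputs from the documents**
- Clinic Check: 2–3 business days after RTS (Section 8.1).
- Phone call: 30 days after RTS (Section 4.1).
- PT allowance: up to 19 visits after the initial evaluation, 20 in total (Sections 8.1 and 4.1).

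**Assumptions**
- RTS is met on a weekday, with Monday–Friday business days and no holidays.
- The initial evaluation is a separate visit, and the Clinic Check counts towards the 19.
- Later PT is once or twice weekly. The documents give no frequency.
- The AE recording period in Section 8.3.4 runs for 90 days after RTS or after the eight-week limit, whichever comes first. This fits the AE evaluations scheduled at 30 and 90 days.

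**Step 1: interval from Clinic Check to call.** RTS on Monday plus 2 business days is calendar day 2. RTS on Wednesday plus 3 business days crosses a weekend and is day 5. Over all weekdays the Clinic Check falls on day c = 2 to 5. The interval is 30 − c: 30 − 2 = 28 days down to 30 − 5 = 25 days.

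**Step 2: does the allowance leave room for later PT?** Visits left after RTS at study visit k are 19 − k − 1 = 18 − k.
- k = 4: 14 left
- k = 8: 10 left
- k = 12: 6 left

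Even a child who uses all 12 study visits could attend PT weekly until the call.

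**Step 3: window covered if the last clinic visit is read literally.** After j weekly PT visits the window is 30 − (c + 7j), and the days not asked about are 7j.

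| Later weekly PT visits (j) | Days covered by the question | Days not asked about |
|---|---|---|
| 0 | 25–28 | 0 |
| 1 | 18–21 | 7 |
| 2 | 11–14 | 14 |
| 3 | 4–7 | 21 |

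If PT continues once or twice weekly up to the call, or until the allowance runs out, about 0–7 days are covered and about 21–28 are not. For example, with k = 12 and twice-weekly PT, the sixth visit falls at c + 6 × 3.5 = c + 21, which is day 23–26 and leaves 4–7 days.

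**Step 4: what else would catch the event?**
- *Starts after the Clinic Check and still present at day 30:* the 90-day survey asks about problems ongoing at the 30-day call, so this is prompted.
- *Starts after the 30-day call:* the 90-day survey asks about it.
- *Starts and resolves between the Clinic Check and the last PT visit:* no scheduled question covers it. The general duty in Section 8.3.4 to document all on-study AEs still applies, but nothing prompts the family.

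**Step 5: with the anchor fixed.** If the question starts at the Clinic Check, the window is 25–28 days for every child who meets RTS and attends that visit, in every arm and whatever the later PT use.

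**The case against.** The case on the other side is substantial.

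- **Intended meaning.** Appendix 12.5 mentions questionnaire copies handed out at the Clinic Check, so its author may have had that visit in mind. A trained therapist asks the question with the AE Log to hand and can clarify it. This stands as evidence of intent, but the words read to families do not say so.
- **Later PT visits are not blind to events.** Section 8.3.4 also says AEs are assessed at each treatment visit and that all on-study events are documented. Section 6.5 has therapists ask about NSAID, brace and ice use at each PT treatment. A therapist may well record an event seen at later PT. It is unclear whether these provisions reach visits after the Clinic Check, and no form or schedule entry requires an inquiry there.
- **Narrow endpoint and early reactions.** Section 3 limits the safety endpoint to iontophoresis- or DSP-related events. Section 2.3.3 names local skin and hypersensitivity reactions as the main concern, and the knee is examined at the Clinic Check. Most such reactions should be seen by then. This stands and limits the impact.

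A reader might infer that persisting reactions go unprompted in every arm. The documents do not support that: the 90-day survey asks about problems ongoing at day 30, and a child without later PT is asked about the whole interval.

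A reader might also infer that the arm with more later PT will look safer. That does not follow either. Faster RTS leaves more of the allowance unused, but better recovery means less need for PT, and Section 3 itself expects faster RTS to limit the number of visits. More contact with therapists could also raise detection.

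**Conclusion.** The point holds as a gap in the wording of the safety follow-up. Because the anchor is undated, the elicited window for children with later PT can shrink from 25–28 days to about 0–7 days if PT continues up to the call. The events left unprompted are those that start and resolve between the Clinic Check and the last PT visit. The window depends on PT use after randomisation and could therefore differ between arms.

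This rests on a literal reading of the script by families and on the assumed PT frequency. It is tempting to turn it into a distortion of AE rates by arm, but that needs the share of children continuing PT in each arm, the rate of events in the interval, and the share missed at PT visits. The documents give none of these, so neither the size nor the direction of any bias can be determined. The effect is probably modest and falls mainly on late or systemic events. The reason to act is that the correction costs almost nothing.

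**What to change.** In Appendix 12.5, anchor the new-problem question, the new-medication question and the unresolved-AE review to *your Clinic Check Visit on [date]*. If there was no Clinic Check, use the date of the last study visit with an AE evaluation. Use identical wording in all three arms. Add one sentence to Section 8.3.4 stating that standard PT visits after the Clinic Check do not reset this date.

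The cost is a change to the phone worksheet and one protocol sentence. The date should already be in the study records, and no visit, procedure or staff time is added. The downside is a recall period of up to about four weeks for children still attending PT, the same as for the other children.

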8.2 SAFETY AND OTHER ASSESSMENTS

The following procedures/evaluations will be obtained by qualified Therapists treating the subjects: Assessed At Enrollment/Randomization Study Treatment Visit 1:

 Inclusion/Exclusion Criteria - Based on the patient's medical history and review of the initial evaluation, the Treating Therapists will determine whether patients meet eligibility criteria for the study.

Note: if radiograph images were obtained to determine skeletal maturity, the Treating Therapist will ensure the results are documented in the radiologist's notes or noted in the physician's notes in the electronic medical record.

- Informed Consent Treating Therapist will conduct the informed consent process as outlined in Section 10.1.1.2 of this document.
- Randomization After a patient signs Consent, the Treating Therapist will assign the patient to the research group per the randomization log at the Site (see section 6.3 Measures to Minimize Bias: Randomization and Blinding).

Assessed at All Study Treatment Visits:

- Brief Physical examination of the affected knee an evaluation made by the treating physical therapist to include: skin color, temperature, presence of edema, turgor, pain with palpation/pressure, changes to skin texture, and integrity. Also assessed at Clinic Check visit.
- Concomitant Medication Review a paper-based form completed by the Treating Therapist to document drug, dose, frequency, start and stop dates, and reason for taking. Also assessed at Clinic Visit Check visit.
- Adverse Event Evaluation a paper-based form completed by the Treating Therapist to document occurrence, severity, relatedness, duration, and expectedness of the event. Subjects receiving iontophoresis will be specifically monitored for possible burns. This data will be captured during the examination of the affected knee as well as for 15 minutes post patch application.

Also assessed at Clinic Visit Check visit, 30-Day Phone Follow Up and electronically at the 90-Day Follow Up (see Appendix 12.6 90-Day Follow Up – Electronic Survey)

• Compliance Checks – a paper-based form completed by the Treating Therapist to assess participant compliance with: study visits, length of time iontophoresis patch worn, home exercise program, icing, activity restriction, and bracing instructions. Also assessed at Clinic Check visit.

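### The 90-day survey's safety questions all start from the 30-day call, so a child who misses that call is not asked about the weeks between the Clinic Check and about day 30

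*Combined protocol and SAP*

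**What the plan says.** Two follow-up contacts come after the clinic phase. Section 4.1 states: "All participants will receive a phone follow-up call 30 days after they meet RTS criteria", and adds an "electronic survey follow-up 90 days after they meet RTS criteria". Before these, section 8.1 places a Clinic Check "Two (2) to three (3) business days after a participant is cleared for RTS", or once eight weeks of treatment have been given, whichever is sooner. For adverse events, section 8.2 lists the contacts beyond the treatment visits: "Also assessed at Clinic Visit Check visit, 30-Day Phone Follow Up and electronically at the 90-Day Follow Up". The schedule in 1.3 puts adverse-event and medication review at the same three points.

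The look-back periods are fixed by the forms. The 30-day call (12.5) asks: "Since your last clinic visit, have you been seen by a doctor or had any new medical problems". The 90-day survey (12.6) has three safety questions with a time reference:

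- ongoing problems: "Did you have any ongoing medical problems at your 30-day Follow Up call";
- new problems: "Since your 30-day follow up call, have you been seen by a doctor or had any new medical problem";
- new medications: "Since your 30-day Follow Up call, have you started any new medications".

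The survey displays no call date and has no branch for a participant who had no call.

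**The concern.** The three contacts form a chain in which each covers the time since the one before. The 30-day call is the only link that covers the time after the Clinic Check. If the call fails, the survey still starts where the call should have been, and the missing stretch passes to no other scheduled question. The survey's reference point is also undefined for that family.

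Safety is a secondary endpoint (section 3), to be compared between arms by GEE (9.4.4). Section 2.3.1.2 says that no data have been published on systemic effects of the drug by this route, and 7.1 foresees that pain may relapse between the Clinic Check and day 90. A problem that starts and resolves in the unasked stretch, or a medication started in it, could go unrecorded. In the dataset, time that nobody asked about would look the same as time without events.

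**Working it through.** The plan states no figure on this point, so the check is a comparison of wording plus date arithmetic.

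**Who asks about which period** (child who meets RTS on day 0):

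| Contact | Nominal time | Period asked about |
|---|---|---|
| Clinic Check (8.1, 8.2, 8.3.4) | 2 to 3 business days after RTS | since the previous visit |
| 30-day call (4.1, 12.5) | day 30 | since the last clinic visit |
| 90-day survey (4.1, 12.6) | day 90 | since the 30-day call |

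Remove the middle row and the period from the Clinic Check to day 30 belongs to no remaining row.

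**Length of the gap.** Assumption: 2 to 3 business days equal 2 to 5 calendar days, depending on weekends.

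- Gap = 30 − day of Clinic Check.
- Clinic Check on day 2: 30 − 2 = 28 days, and 28/90 = 31% of the 90 days after RTS.
- Clinic Check on day 5: 30 − 5 = 25 days, and 25/90 = 28%.

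**Does another provision close it?**

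- Section 7.3 (lost to follow-up) sets out contact steps when a participant does not come back to the clinic for a required visit. It does not mention a missed telephone call.
- Section 10.1.8.1 provides for a telephone contact after the survey, but only for new adverse events, or new medications possibly linked to one, that have been identified. It cannot be relied on to recover something the survey did not ask about.
- Section 8.1 allows further physical therapy visits after the Clinic Check. They are optional, and neither 1.3 nor 8.2 lists them as adverse-event assessments.

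**What the Clinic Check does cover.** Adverse events, medications and a brief knee examination are all reviewed there, so the first 2 to 5 days after RTS are asked about. At the maximum of two patches per week (6.1.1), 12 patches take 12/2 = 6 weeks. If RTS is not met, the Clinic Check follows week 8, so about 8 − 6 = 2 weeks after the last patch are covered.

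**The case against.** The strongest reply is that the gap needs several things at once: a call that is never completed, a survey that is nevertheless returned, and a new event in the window that staff do not learn of otherwise. Section 12.5 provides optional reminder emails and sets no latest date for the call, and a late call would close the gap because its question runs from the last clinic visit. A problem still present around day 30 might be reported under the ongoing-problem question. Children may also still be attending therapy, or be treated for a relapse by the same therapist who keeps the adverse-event log, and 8.3.4 requires all adverse events on study to be documented. All of this stands, and it makes loss possible rather than certain. None of it is a scheduled question about the period.

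It is also fair that 8.3.4 is unclear about when collection ends, since it takes the shorter of two periods, one of them tied to eight weeks of treatment. The schedule and 8.2 nevertheless plainly provide for review at both follow-ups.

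A reader might infer more than the documents support:

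- *That such a child is never asked about the weeks right after the last patch.* The Clinic Check covers the first days, and about two weeks for a child who finishes 12 patches in six weeks without meeting RTS.
- *That 15% of 147, about 22 children, are affected.* The 15% in section 9.2 is a non-compliance allowance for the sample size, not a missed-call rate. Some children who miss the call will not return the survey either, and rewording cannot help them.
- *That delayed skin reactions would be missed.* Section 2.3.1.1 describes rare, transient reactions and 2.3.3 calls local reactions self-limited.
- *That the loss differs by arm.* Nothing in the documents shows different call completion between groups.

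**Conclusion.** The point holds in a limited form. Followed as written, the forms leave the period from the Clinic Check to about day 30 unasked for a child who misses the call but returns the survey. The window of 25 to 28 days rests on the calendar-day conversion above, on nominal visit timing, and on a child who met RTS and had the Clinic Check. The number of children cannot be computed because no missed-call rate is given. The consequence is possible under-recording of transient events and of new medications for a secondary safety endpoint. The primary endpoint and the sample size are unaffected. Severity is low: a desirable improvement, not a condition for the trial to proceed.

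**What to change.** Anchor all three survey questions to the date of the participant's last completed adverse-event and medication review: the 30-day call if it took place, otherwise the Clinic Check or last study visit. Pre-fill that date from REDCap. The new-problem and new-medication questions would open with 'Since [date]', and the ongoing-problem question would ask about problems present 'on [date]', with the rest of each question unchanged. The call date is already recorded under 12.5, and 10.1.8.1 has study data entered in REDCap.

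The anchor should not be the last contact of any kind. An optional therapy visit after the Clinic Check is not a scheduled safety review, and using its date would reopen the gap.

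The cost is an edit to one electronic form and its appendix copy, with IRB approval. A child without a call would have a recall period of 85 to 88 days (90 − 5 and 90 − 2) instead of 60 (90 − 30), which is less precise but better than no question. If the trial is already under way, recall wording will change part-way through, so the form version used by each participant should be recorded.
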